4 STUDY SCHEDULE

The total study duration for each subject consists of pre-screening, screening, treatment, and follow-up periods. A study flow diagram is presented in [Figure 4-1](#).

- (1) Pre-Screening Period:** A separate Informed Consent Form (ICF) will be used for the pre-screening. The pre-screening period is designed for evaluation of histologically or cytologically confirmed locally advanced or metastatic solid tumors and CCR5 positive status by Immunohistochemistry (IHC) assay. This assay will be performed in archival tissue from previous biopsy specimens. If archival tissue is not available then, fresh core or excisional biopsy will be done. If patient qualifies, then they will undergo full screening.
- (2) Screening Period:** Screening assessments will commence after obtaining signed informed consent, and will include review of medical and medication history, demographic information and baseline disease characteristics, eligibility evaluation, physical examination, vital signs, height and weight, concomitant medications, electrocardiogram (ECG), tumor imaging assessment (prior imaging assessment within the last 3 months of the Screening Visit is acceptable), routine serum biochemical, hematologic, urinalysis, serum pregnancy (if applicable). These assessments must be conducted within 28 days of the first treatment visit.
- (3) Treatment Period:** Subjects who meet the eligibility criteria will have completed following evaluations and assessments before receiving treatment: a) review of medical and medication history; b) physical examination, vital signs and documentation of ECOG performance status; c) ECG; d) routine serum biochemical, hematologic, urine pregnancy (if applicable) and urine laboratory assessments. Additionally, a blood sample will be collected prior to treatment administration for CTC and CAML analysis.

Leronlimab (PRO 140) will be administered subcutaneously weekly by a licensed medical professional at clinic site or self-administered by subjects at home.

***Note:** All initial leronlimab (PRO 140) SC weekly injections must be administered at clinic. The remaining study treatment injections may be self-administered by subjects at home after proper training by a healthcare professional.*

Subjects will be allowed to continue treatment until any one of the following occurs: progressive disease or unacceptable toxicity or withdrawal of consent.

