Ironlimab (PRO 140) administration [15]																										
Post Injection Site Evaluation by Investigator [16]																										
Injection Site Pain Assessment [17]																										
Survival status																										
Concomitant medications	X	X	X	X	X	X	X	X	X	X	X	X	X	X	X	X	X	X	X	X	X	X	X	X		
Adverse Events	X	X	X	X	X	X	X	X	X	X	X	X	X	X	X	X	X	X	X	X	X	X	X	X		

Footnotes

- [1] A separate Informed Consent Form (ICF) will be used for the pre-screening. The pre-screening period is designed for evaluation CCR5 positive status by Immunohistochemistry (IHC) assay. This assay will be performed in archival tissue from previous biopsy specimens. If archival tissue is not available then, fresh core or excisional biopsy will be done. If patient qualifies, then they will undergo full screening.
- [2] Informed consent must be obtained prior to patient participation in any protocol-related activities that are not part of routine care.
- [3] A complete review of the subject's past medical history, past surgeries, and current therapies (medications and non-medications) will be undertaken by the Investigator to check that all inclusion and no exclusion criteria have been met.
- [4] Vital signs include blood pressure, heart rate, respiration rate, and temperature will be measured at clinic visit.
- [5] Weight only
- [6] Symptom-directed physical examination at clinic visits
- [7] A 12-lead ECG will be repeated during the study only if clinically indicated and at the discretion of the treating physician.
- [8] Prior tumor imaging assessment within the last 3 months of the Screening Visit is acceptable. During the Treatment Phase, scans are to be done approximately every 3 months or according to institution's standard practice by CT, PET/CT or MRI with contrast (per treating investigator's discretion) using the same method as at baseline. Tumor measurements will be done using RECIST v1.1. To be assigned a status of PR or CR,

changes in tumor measurements must be confirmed by repeat assessments that should be performed 4-8 weeks after the criteria for response are first met. In the case of SD, measurements must have met the SD criteria at least once after study entry at a minimum interval of 4-8 weeks.

[9] Hemoglobin, Hematocrit (HCT), Red Blood Cells (RBC), White Blood Cells (WBC) with total and differential count, absolute lymphocyte count, absolute neutrophil count (ANC) and platelets.

[10] Serum Biochemistry will include:

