4.4 FOLLOW-UP PERIOD

Duration of Follow Up

- An End of Treatment (EOT) visit will be conducted 30 (\pm 3) days after the last treatment visit (i.e., after last dose of leronlimab (PRO 140)).
- All patients will be followed for adverse events for 30 days after last dose of leronlimab (PRO 140) or until the patient starts a new treatment, whichever occurs first.
- Subjects who discontinue treatment for unacceptable adverse event(s) will be followed until resolution or stabilization of the adverse event (i.e. the grade is not changing).
- If a subject stops treatment due to unacceptable adverse event(s) but has not demonstrated disease progression, then the subject will be followed with imaging studies every 9 weeks until the time of progression radiographically according to RECIST v1.1 criteria. In the event that a radiographic response is detected, then this event will be included as a response in the final analysis, and the time of progression used in calculation of the survival analysis.
- Subjects will be followed up by clinic visits or phone call or another method of contact, for survival status every 3 months (\pm 1 month) for 2 years after treatment discontinuation or until death, whichever occurs first.

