Imaging scans to be done approximately every 3 months or according to institution's standard practice.

- Time to new metastases (TTNM);

Note: Recorded time from baseline metastatic disease (at time of enrollment) to the time of development of new metastasis in different site. New metastases in same site will be also recorded.

- The change from baseline in circulating tumor cells (CTC) level in the peripheral blood.

Note: Reported unit of measure will be the number of CTCs/milliliter. CTCs enumeration will be performed at baseline and at the time of response assessment. Fraction of baseline positive and change from ≥ 5 CTCs will be recorded and reported.

- Overall survival defined as time in months from the date of first study treatment to the date of death;

Note: Patients will be followed from the start of treatment until 2 years post-treatment or death, whichever occurs first, and average survival time will be measured.

Exploratory Outcome (Endpoints) Measures:

- Measure immune biomarkers in CTCs, metastatic tissue and immune cells such as CAML and correlate with therapeutic benefit (PFS); and
- Assess changes in CTCs and CAML after treatment and perform correlative analysis of CCR5 expression.

PFS will be calculated using Kaplan-Meier curves and the median PFS will be read from this curve. Response rates (overall response rate, clinical benefit rate) will be calculated using proportions and 95% confidence intervals. Time to new metastases and overall survival will also be analyzed using Kaplan-Meier curves. Exploratory serial blood markers will be related to PFS using Cox regression, and to response using logistic regression.

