2.7 Outcome Measures

2.7.1 Efficacy Outcome Measures

The efficacy outcome measures in this study are:

- Progression free survival (PFS) defined as time in months from the date of first study treatment to the date of disease progression or death from any cause, whichever comes first.

Note: All patients who receive at least one dose of leronlimab (PRO 140) will be included in the primary analyses of PFS. The Response Evaluation Criteria in Solid Tumors (RECIST v1.1) criteria will be used for objective tumor response assessment (when disease is measurable and non-measurable);

The time in months from start of treatment to progression or death will be measured for all patients who receive at least one dose of study drug. Patients will be followed up to 2 years after completion of treatment.

- Overall response rate (ORR, defined as Complete Response (CR) + Partial Response (PR)), and clinical benefit rate (CBR, defined as CR + PR + Stable Disease (SD)) in subjects with CCR5+ locally advanced or metastatic solid tumors treated with leronlimab (PRO 140)

Note: Overall response rate is defined as the proportion of patients who achieve an overall response of complete response or partial response in the total number of evaluable patients, assessed by RECIST v1.1. Clinical benefit rate is defined as the proportion of patients who achieve an overall response of complete response or partial response or stable disease in the total number of evaluable patients, assessed by RECIST v1.1. Imaging scans to be done approximately every 3 months or according to institution's standard practice.

- Time to new metastases (TTNM);

Note: Recorded time from baseline metastatic disease (at time of enrollment) to the time of development of new metastasis in different site. New metastases in same site will be also recorded.

- The change from baseline in circulating tumor cells (CTC) level in the peripheral blood.

Note: Reported unit of measure will be the number of CTCs/milliliter. CTCs enumeration will be performed at baseline and at the time of response assessment. Fraction of baseline positive and change from ≥ 5 CTCs will be recorded and reported.

- Overall survival defined as time in months from the date of first study treatment to the date of death;

Note: Patients will be followed from the start of treatment until 2 years post-treatment or death, whichever occurs first, and average survival time will be measured.

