7.10.6 Time to new metastases (TTNM)

Time to new metastases (TTNM) will be calculated according to the formula noted below:

$$\text{Time to new metastases (TTNM)} = (\text{Date of new metastases} - \text{Date of first treatment}) + 1$$

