8.2.1.3 Time to new metastases (TTNM)

The Time to new metastases will be calculated using the formula in [Section 7.10.6](#) and summarized descriptively.

The likelihood score test in the Cox proportional hazards model (which is the equivalent of the Log Rank test) will be used to compare the time to new metastases between the treatment groups. Kaplan-Meier analysis will be used to depict the median time (days) to new metastases.

The proportion of new metastases will be presented and summarized descriptively.

8.2.1.4 Change from baseline in circulating tumor cells (CTC) level in the peripheral blood

The change from baseline in circulating tumor cells (CTC) level in the peripheral blood will be summarized descriptively and will be compared using ANCOVA.

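### Time to new metastases is analysed by Kaplan-Meier with no censoring rule and no allowance for death as a competing event, so its curve and median can mislead

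*SAP*

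**What the plan says.** Both documents use Kaplan-Meier. SAP 8.2.1.3 states that "Kaplan-Meier analysis will be used to depict the median time (days) to new metastases"; Protocol 8.7.3 states that "Time to new metastases and overall survival will also be analyzed using Kaplan-Meier curves". The SAP adds a crude summary: "The proportion of new metastases will be presented and summarized descriptively".

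The event is a new metastasis only. SAP 2.7.1 describes TTNM as "Recorded time from baseline metastatic disease (at time of enrollment) to the time of development of new metastasis in different site", with same-site metastases recorded as well. The formula in SAP 7.10.6 is date of new metastases minus date of first treatment, plus 1. It gives no date for patients without the event. PFS, by contrast, expressly includes death from any cause.

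The scan schedule matters too. On treatment, "scans are to be done approximately every 3 months" or by site practice (Protocol Table 4-1, footnote 8). Treatment has a stated end: "Subjects will be allowed to continue treatment until any one of the following occurs: progressive disease or unacceptable toxicity or withdrawal of consent". The end-of-treatment visit (Protocol 4.4.1) lists no tumor imaging. Later imaging is described only for subjects who stop for an adverse event without progression: "the subject will be followed with imaging studies every 9 weeks until the time of progression radiographically according to RECIST v1.1 criteria". Protocol 7.15.6 makes an exception to stopping at progression, for patients with an initial disease flare.

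**The concern.** Kaplan-Meier treats a censored patient as someone who will go on to have the event at the same rate as those still observed. A patient who has died cannot. Deaths without a recorded new metastasis are to be expected in advanced or metastatic disease, and the plan does not say how they enter the TTNM analysis. If they are censored, 1-KM is not the probability of a new metastasis, and the Kaplan-Meier median need not be a time by which half the patients have had one.

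Patients whose existing lesions grow raise a different problem. They can still develop a new metastasis, but most leave scheduled scanning, and for a reason tied to prognosis. That is not the independent censoring Kaplan-Meier requires.

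TTNM is the listed outcome closest to the anti-metastatic rationale in Protocol 1.2. SAP section 5 plans no formal hypothesis test, so the descriptive curve and median are the TTNM result.

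**Working it through.** The documents state no TTNM rate, median or event count, so there is no planned figure to reproduce. All hazards below are assumptions, constant over time and per month.

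**Formulas.** With hazard h1 for new metastasis and h2 for the competing event:

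- 1-KM(t) = 1 - exp(-h1·t)
- cumulative incidence(t) = h1/(h1+h2) × [1 - exp(-(h1+h2)·t)]
- KM median = ln 2 / h1
- proportion who ever have the event = h1/(h1+h2)

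**Worked case.** Take first-event TTNM, with h1 = 0.05 and h2 = 0.10 (death or existing-lesion progression). At 12 months 1-KM = 1 - exp(-0.60) = 45%. The cumulative incidence is (0.05/0.15) × [1 - exp(-1.80)] = 28%.

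| TTNM definition | h1 | h2 | 12-month 1-KM | 12-month cumulative incidence | KM median (months) | Ever have event |
|---|---|---|---|---|---|---|
| First progression event | 0.05 | 0.10 | 45% | 28% | 13.9 | 33% |
| First progression event | 0.06 | 0.06 | 51% | 38% | 11.6 | 50% |
| Any before death | 0.05 | 0.01 | 45% | 43% | 13.9 | 83% |
| Any before death | 0.05 | 0.05 | 45% | 35% | 13.9 | 50% |

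The last two rows count death alone as competing and suppose that scanning continues after progression.

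**How often a median appears for a minority event.** For each setting, 2,000 trials of 30 patients were simulated. Scans were every 3 months, the cut-off was 36 months, and observation ended at progression or death. Assumed median PFS was 3, 4 or 6 months. A Kaplan-Meier median was reached although fewer than half the patients had a new metastasis in:

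- 44-50% of trials when new metastases were 20% of first events
- 72-75% at a 30% share
- 75-79% at a 40% share
- 42-44% at a 50% share

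**Direction of bias from stopping scans at progression.** Take median PFS 4 months, so the total hazard is ln 2 / 4 = 0.173. Let 30% of first events be new metastases, and 30% of the remainder deaths. The hazards are then 0.052 (new metastasis), 0.036 (death) and 0.085 (existing-lesion progression). Censoring at progression or death gives a 12-month 1-KM of 46%. As a first event, the cumulative incidence is 26%. The risk of any new metastasis before death, including after progression, depends on what follows progression. It is 38%, 46% or 52% if the hazard of new metastasis is then 1, 2 or 3 times its earlier value (death hazard unchanged). Against that target, 1-KM is too high, about right, or too low.

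**The case against.** A reader might infer that the plan simply overstates the chance of new metastases, or that most patients will never have one. The documents do not support either. Growth of an existing lesion does not prevent a new metastasis, so counting it with death is right only for first-event TTNM. The plan's definition does not impose that. The 28% and 33% figures depend on it. With death alone competing, the assumed 12-month gap is 2 to 10 percentage points, and 50% to 83% of patients eventually have the event. Entry requires ECOG 0-1 and a life expectancy of at least 6 months, so a low early death rate is plausible.

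Three further points stand. Censoring at death is the customary reading, not the plan's text; the documented gap is the missing rule. Scanning need not end at progression for patients treated beyond it under Protocol 7.15.6. The crude proportion is not inflated in this way, and its difference from a Kaplan-Meier median is no contradiction, because they are different quantities.

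TTNM is also one of several efficacy outcomes in a single-arm study of up to 30 patients, and no decision rule uses its median. That limits the weight of the point but does not remove it.

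**Conclusion.** The point holds in a limited form. The plan applies Kaplan-Meier to an event that excludes death, with no censoring rule and no competing event. If deaths are censored, 1-KM overstates cumulative incidence relative to death, and a median can be reported when fewer than half the patients have the event. The size rests on assumed constant hazards: at 12 months, 45% against 28% for first-event TTNM, or 45% against 43% to 35% with death alone competing. For the end of scanning at existing-lesion progression, the direction of bias cannot be settled from the documents unless TTNM is restricted to first events. This should be corrected before analysis, but it does not undermine the trial.

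**What to change.** Amend SAP 7.10.6 and 8.2.1.3 and Protocol 8.7.3.

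1. Define TTNM as new metastasis in a different site as the first progression event, censored at the last tumor assessment if alive and progression-free. Say openly that this narrows the endpoint. State where a new same-site lesion falls, since it is RECIST progression but not a different-site event.
2. Replace Kaplan-Meier by the Aalen-Johansen cumulative incidence, with death and existing-lesion progression as competing events. Report 6- and 12-month incidence with 95% CIs.
3. If any new metastasis before death is kept as the endpoint instead, treat only death as competing. State that censoring when scanning ends after progression may bias the estimate in either direction.
4. Report a median only if the cumulative incidence reaches 50%. Keep the crude proportion, labelled as a count that ignores incomplete follow-up.

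The cost is wording and a standard SAS option, with no new data; SAP section 12 describes the document as a first draft. The downsides are that a simple TTNM median may be lost and that the first-event definition answers a narrower question.

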3 STUDY DESIGN

This is a multicenter study that will enroll up to 30 subjects. The target population for this study is subjects with histologically or cytologically confirmed diagnosis of CCR5+, locally advanced or metastatic solid tumors. A study flow schematic is presented in **Figure 3-1**.

Figure 3-1: Study Schematic

Note: Scans are to be done approximately every 3 months or according to institution's standard practice by CT, PET/CT or MRI with contrast (per treating investigator's discretion) using the same method as at baseline.

This is a single arm study with 30 patients of leronlimab (PRO 140) patients with CCR5+ locally advanced or metastatic solid tumors.

Leronlimab (PRO 140) will be administered subcutaneously as weekly dose of 525 mg until disease progression or intolerable toxicity. Subjects participating in this study will be allowed to receive/continue standard-of-care chemotherapy or radiotherapy as per the dosing schedule included on the package insert.

Patients will be evaluated for tumor response approximately every 3 months or according to institution's standard practice by CT, PET/CT or MRI with contrast (per treating investigator's

discretion) using the same method as at baseline. Tumor measurements will be done using RECIST v1.1.

Note: Subjects participating under Protocol version 1.0 received 350 mg of PRO 140. Dose was increased from 350 mg to 525 mg weekly under version 2.0 of this protocol.

Subjects enrolled under version 1.0 have the option of remaining on their current dose of 350mg or increasing their dose to 525 mg for the remainder of the trial.

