8.1 TREATMENT GROUPS

- 525 mg leronlimab (PRO 140)

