8.6.2. Covariates

For efficacy analyses, the baseline values will be used as covariates in the analysis models. Other important prognostic factors will be specified in the SAP for the study.

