2. PROTOCOL DESIGN

2.1 Design Overview

This is a single arm study with 30 patients of leronlimab (PRO 140) in patients with CCR5+ locally advanced or metastatic solid tumors.

Leronlimab (PRO 140) will be administered subcutaneously as weekly dose of 525 mg until disease progression or intolerable toxicity. Subjects participating in this study will be allowed to receive/continue standard-of-care chemotherapy or radiotherapy as per the dosing schedule included on the package insert.

In this study, patients will be evaluated for tumor response approximately every 3 months or according to institution's standard practice by CT, PET/CT or MRI with contrast (per treating investigator's discretion) using the same method as at baseline. Tumor measurements will be done

using RECIST v1.1.

The total study duration for each subject consists of pre-screening, screening, treatment, and follow-up periods. A study flow diagram is presented in Figure 2-1.

(1) Pre-Screening Period: A separate Informed Consent Form (ICF) will be used for the pre-screening. The pre-screening period is designed for evaluation of histologically or cytologically confirmed locally advanced or metastatic solid tumors and CCR5 positive status by Immunohistochemistry (IHC) assay. This assay will be performed in archival tissue from previous biopsy specimens. If archival tissue is not available then, fresh core or excisional biopsy will be done. If patient qualifies, then they will undergo full screening.

(2) Screening Period: Screening assessments will commence after obtaining signed informed consent, and will include review of medical and medication history, demographic information and baseline disease characteristics, eligibility evaluation, physical examination, vital signs, height and weight, concomitant medications, electrocardiogram (ECG), tumor imaging assessment (prior imaging assessment within the last 3 months of the Screening Visit is acceptable), routine serum biochemical, hematologic, urinalysis, serum pregnancy (if applicable). These assessments must be conducted within 28 days of the first treatment visit.

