2.7.3 Exploratory Outcome Measures

- Measure immune biomarkers in CTCs, metastatic tissue and immune cells such as CAML and correlate with therapeutic benefit (PFS); and
- Assess changes in CTCs and CAML after treatment and perform correlative analysis of CCR5 expression

3. Sample Size Determination, Statistical Power, And Significance Level

This is a multicenter study and up to 30 subjects will be enrolled in this study. The sample size for is based on clinical judgment. No statistical power calculation is used to establish the sample size.

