7.7 Multiple Comparisons and Multiplicity

There will be no adjustment for multiple testing or multiplicity for this phase II trial. For all effectiveness endpoints, inference will be based on type I error rate of 0.05.

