7.8 Covariates and Prognostic Factors

In the efficacy analysis, the baseline values will be used as covariates in the analysis of all efficacy outcome measures.

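### The ANCOVA planned for CTC change has no defined comparison in a single-arm trial, and if it is used to test mean change against zero its standard error is generally too small

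*SAP*

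**What the plan says.** SAP 8.2.1.4 gives the whole method for CTC change in one sentence: it "will be summarized descriptively and will be compared using ANCOVA". It does not say what is compared with what, at which visit, or on which scale.

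The covariate comes from SAP 7.8, under which "the baseline values will be used as covariates in the analysis of all efficacy outcome measures". Protocol 8.6.2 agrees: "For efficacy analyses, the baseline values will be used as covariates in the analysis models".

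The design has one group. SAP 2.1 states: "This is a single arm study with 30 patients of leronlimab (PRO 140) in patients with CCR5+ locally advanced or metastatic solid tumors". Protocol 8.1 lists a single treatment group, at 525 mg. Protocol 3 adds a note: "Subjects participating under Protocol version 1.0 received 350 mg of PRO 140". Those subjects could stay on 350 mg or move to 525 mg. The SAP does not mention 350 mg.

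On testing, SAP 7.7 says: "For all effectiveness endpoints, inference will be based on type I error rate of 0.05". SAP 5 says that the study has no formal hypothesis testing. On size, SAP 3 says: "No statistical power calculation is used to establish the sample size".

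On timing, SAP 2.7.1 places CTC counts at baseline and at response assessment. Protocol 7.11 draws the samples at T1, every 3 weeks after that, and at end of treatment.

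**The concern.** Adjusting for baseline is useful when two arms are contrasted. Here there is only one. A programmer following SAP 8.2.1.4 either finds that the comparison cannot be run or has to choose some other output of the model.

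The obvious choice is the least-squares mean change at the average baseline, set against zero. The point estimate is harmless, since it equals the raw mean change. The standard error is the problem. It uses only the scatter left after regression on baseline, as if the sample's mean baseline were a known constant. A sample whose baseline happens to be high will tend to show a fall through regression to the mean, and the model does not count that source of variation.

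At stake is the interval, and any p-value, for a measure that Protocol 1.2.2 treats as an indicator of treatment efficacy, in a trial with no control arm to show what change would have occurred anyway.

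**Working it through.** **No figure to reproduce.** The 0.05 in SAP 7.7 is a nominal level. The documents derive no sample size, SD or power for CTC.

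**Inputs from the documents:** one arm; up to 30 subjects; level 0.05 (two-sided assumed, as sidedness is not stated); change defined as post-baseline minus baseline (SAP 7.10.3). **Assumed, because the documents give nothing:** baseline-to-follow-up correlation r from 0 to 0.9; ratio k of follow-up SD to baseline SD from 0.5 to 2; normal or skewed data.

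**Formula.** Let s be the baseline SD and let the true mean change be zero.

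- True variance of the mean change: s²(1 + k² − 2rk)/n.
- Variance the ANCOVA uses for the adjusted mean: s²k²(1 − r²)/n.
- Ratio: R = k²(1 − r²)/(1 + k² − 2rk).
- Actual two-sided error: 2[1 − Φ(1.96√R)].

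The denominator of R minus its numerator is 1 − 2rk + r²k² = (1 − rk)². So R never exceeds 1, and it equals 1 only when rk = 1. The standard error is right in that one case and too small otherwise.

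**Equal SDs (k = 1).** R reduces to (1 + r)/2. The last column is a simulation with normal data, n = 30 and 100,000 replicates.

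| r | R | √R | Error, formula | Error, simulated |
|---|---|---|---|---|
| 0 | 0.50 | 0.707 | 16.6% | 15.8% |
| 0.3 | 0.65 | 0.806 | 11.4% | 10.9% |
| 0.5 | 0.75 | 0.866 | 9.0% | 8.8% |
| 0.7 | 0.85 | 0.922 | 7.1% | 6.9% |
| 0.9 | 0.95 | 0.975 | 5.6% | 5.6% |

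A paired t-test on the same data rejected 4.9–5.1% of the time.

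**Unequal SDs.** Two worked cases:

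- k = 2, r = 0.5: R = 4 × 0.75/(1 + 4 − 2) = 1, so the error is 5%. Simulated: 5.0%.
- k = 0.5, r = 0.9: R = 0.25 × 0.19/(1 + 0.25 − 0.9) = 0.0475/0.35 = 0.136, √R = 0.368, so the error is 2[1 − Φ(0.722)], about 47%. Simulated: 45.7%.

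Simulated ranges over r = 0 to 0.9 (n = 30): k = 0.5, 32–46%; k = 0.75, 14–23%; k = 1.5, 4.9–9.9%; k = 2, 5.0–14.1%. The paired t-test stayed at 4.9–5.3%.

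**Skewed data (n = 30, same distribution at both times).** Skew is plausible. The prognostic threshold in Protocol 1.2.2 is 5 cells per 7.5 mL, which is 5/7.5 = 0.67 per mL on the reporting scale, and counts cannot fall below zero.

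| Data | ANCOVA mean against zero | Paired t-test |
|---|---|---|
| Negative binomial, raw | 9.6–17.8% | 4.3–4.6% |
| Lognormal, raw | 12.9–20.2% | 3.7–4.0% |
| Negative binomial, log(1 + count) | 5.4–15.3% | 4.6–5.1% |

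**Direction.** With normal data, r = 0.5 and k = 1, rejections split evenly between apparent rises and apparent falls (4.2% and 4.3%). In a run with over-dispersed raw counts they leaned towards falls (9.9% against 2.3%).

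**Other outputs of the model.** The intercept estimates the change at a baseline of zero cells, which is not the mean change. In the skewed scenarios it rejected from about 9% to 98% of the time. A true two-group ANCOVA contrast (5 v 25 or 15 v 15) held its level, at 5.0–5.2%.

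**The case against.** The strongest reply is that the SAP never says that mean change is tested against zero. SAP 8.2.1.4 mentions neither zero nor an adjusted mean. The PFS, TTNM and survival sections around it all compare treatment groups, so the ANCOVA sentence reads like two-arm wording carried over. Two dose levels did exist, and a contrast between them would keep its 5% level. This stands as far as it goes: the test against zero is one reading. It does not rescue the text. A dose contrast is not planned anywhere, the SAP does not recognise a 350 mg group, and subjects could change dose, so group membership is undefined.

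The second reply is that SAP 5 rules out formal testing. That carries weight, but SAP 7.7 sets an inferential level for all effectiveness endpoints, and SAP 8.3 excludes inferential statistics for safety only. The two positions conflict. Even without a p-value, an interval from the model would carry the same standard error.

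The third reply concerns importance. The heading of SAP 8.2.1 covers every efficacy measure, and only PFS is tied to primary analyses (SAP 2.7.1). A reader might infer that the trial's main result is affected. The documents do not support that: CTC change is one of several measures in an unpowered study.

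**Conclusion.** The point holds in a conditional form. What is on the page is an ANCOVA with no defined comparison in a one-arm trial, and an SAP that contradicts itself on whether CTC is tested. If the model is used to test adjusted mean change against zero, its standard error is generally too small: the error is about 16%, 9%, 7% and 5.6% at r = 0, 0.5, 0.7 and 0.9 with normal data and equal SDs. It is near 5% when rk is close to 1, exceeds 40% in the worst case at k = 0.5, and was about 10–20% with skewed raw counts.

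Two stronger readings are tempting. One is that the plan commits to a test with a fixed inflated error, such as 7–18%. It does not: the comparison is unstated, and every such figure rests on a correlation, SD ratio and distribution that the documents do not supply. The other is that the error favours leronlimab. The interval is too narrow in both directions, and it leans towards apparent decline only if raw counts are skewed. Severity is modest, but the text should be corrected before analysis.

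**What to change.** In SAP 8.2.1.4, replace ANCOVA with a within-patient paired analysis at one named post-baseline visit. This also settles the mismatch between response-assessment timing (SAP 2.7.1) and 3-weekly sampling (Protocol 7.11). Choose one of:

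- paired mean change on log(count + 1) with a 95% CI, stating whether the 1 is added to the raw count or to the per-mL value; or
- a Wilcoxon signed-rank test with the Hodges-Lehmann pseudomedian and its 95% CI. The pseudomedian should be named as such, since with skewed changes it need not equal the median change.

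Report the result as descriptive, in line with SAP 5, and reword SAP 7.7 so that the two sections agree for CTC. In SAP 7.8 and Protocol 8.6.2, state that the baseline-covariate rule does not apply to single-group CTC change.

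The cost is wording. SAP 12 describes the document as a first draft, and the protocol change is one line. No data collection changes. The downside is an interval that will usually be wider, and correct.
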